months. V_A and D_L were not associated with GA, mechanical ventilation or oxygen therapy suggesting that in the absence of extreme prematurity and BPD, prematurity itself does not impair lung parenchymal development. However, further analysis of the preterm infants demonstrated that both V_A and D_L were significantly higher (by about 16%) for infants who received any CPAP in the NICU compared to those who had not received any CPAP (Table 1). This was not a controlled trial of CPAP, but our findings suggest that mechanical stretch from CPAP in preterm infants may produce larger, more functional lungs.

Table 1. V_A and D_L in Healthy Preterm Infants According to CPAP Treatment

Lung Function Measures	No CPAP (n=29)	CPAP (n=19)	P value	% difference
V _A (mL)	606.8 ± 171.5	694.6± 205.2	0.046	16%
D _L (mL/min/mmHg)	3.86 ± 0.97	4.49± 1.42	0.007	16%

Values are Mean ± SD; p values adjusted for length and gender

b3c. Pilot Study: The Effect of eCPAP on FRC through NICU discharge, a RCT

We recently published a pilot study randomizing stable preterm infants \leq 32 weeks of gestation at birth and requiring \geq 24 hours of CPAP for respiratory distress to 2 extra weeks of CPAP (eCPAP) versus CPAP discontinuation when CPAP stability criteria were met¹⁶. CPAP stability criteria included: on CPAP of 4-5 cm H₂O; on room air; respiratory rate \leq 70 breaths/minute, retraction score \leq 1; < 3 self resolving apneas (< 20 seconds) and/or bradycardia (< 100 bpm) and/or desaturations (pulse oximeter oxygen saturation, SpO2 <86%) in 1 hour for past 6 hours; average SpO2 >86% for 90% of the time over the past 24 hours, not being treated for a PDA or sepsis, and tolerating time off CPAP during routine care (up to 15 minutes).

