No studies have compared V_A at 6 month of age in stable preterm infants randomized to eCPAP versus dCPAP in the NICU. Data from our pilot eCPAP study showed a 12% higher FRC in stable preterm infants randomized to eCPAP versus dCPAP at the end of the two week treatment period¹⁶. A study by [name] et al reported a 16% difference in both V_A and D_L in preterm infants according to CPAP treatment in the NICU (Table 1)¹⁵ and a 12% difference in D_L between infants with BPD versus healthy term infants⁶⁹. Therefore, we powered our randomized trial to detect a 12% difference in V_A between the eCPAP and dCPAP groups.

Using an ANCOVA model and assuming a mean V_A of 642 mL (SD=189) based on data of the overall mean and SD from the control and CPAP groups reported in Assaf et al¹⁵, a sample size of 34 infants per group is needed to yield 80% power for detecting a 12% difference (effect size=0.42) in V_A in the eCPAP group at α =0.05 (Table 3). This sample size also allows us to detect a 12% difference in D_L with an effect size of 0.42. We estimate that 18% of the study samples will be twin pairs based on our pilot eCPAP study. Conservatively counting just one infant out of each twin pair for the sample size estimation, we will need 38 infants per group (76 total infants at 6 months) with completed V_A outcomes. We further conservatively project a 10% loss in the NICU and a 15% loss from NICU discharge to the 6 month PFT (due to preterm population and need to be at least 3 weeks after a respiratory infection for the performance of the PFT) and therefore we project we will

Table 3. Estimated power for 34 infants per group with completed PFT data

[figure not shown]
		Mean (SD) in	Estimated Power for Group Difference		
Outcome Measures		Control Group	12%	15%	17%
Alveolar volume (V _A)	Primary Outcome	642 (189)	80	92	97
Lung diffusing capacity (D _L)	Secondary Outcome	4.1 (1.19)	80	92	98

need to randomize 50 infants per group (total n=100) into the trial. This sample size will provide 80% power for detecting an effect size difference of 0.42 in outcome measures between the two groups in Aim 1 (primary outcome of V_A) and Aim 2 for D_L . This sample size allows us to detect a 23% difference in FEF₅₀. Figure 12 shows the projected study recruitment to achieve the desired sample size based on recruitment and cohort

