General linear mixed models (GLMMs) will be used to compare the primary outcomes of alveolar volume (V_A) between the eCPAP and dCPAP while adjusting for the design factor gestational age at delivery (28 and 6/7 and 29 and 0/7 weeks) and other baseline variables that are found to be statistically different between the two groups. Since the lung function measures are highly dependent on infant length and sex, we will further adjust for length and sex in the GLMMs. In order to adjust for intra-twin correlations, generalized Estimating Equations (GEEs) with the linear link function will be used to model $V_{A...}$ The GLMMs can be performed using the GEE estimation approach. Intention to treat analysis will be used for all aims as the primary analysis. The intention to treat population is defined as all randomized infants and the analysis uses the assigned randomization group even if infants did not complete the intervention. In addition, a per protocol analysis will be completed for all aims. The per protocol population is defined as all infants who successfully completed the treatment arm to which they were assigned.

b2. Specific Aim 2 (Secondary Outcomes)

Lung diffusion (D_L) and FEF₅₀ will be will be analyzed with the same general approaches described for the primary outcome in SA #1.

b3. Specific Aim 3 (Exploratory Outcomes)

Logistic regression models will be used to compare the incidence of wheeze and the incidence of wheeze and cough between the two groups adjusting for GA at delivery (<29 vs ≥ 29 weeks). Neurodevelopmental scores will be analyzed with the same general approaches described for the primary outcome in Specific Aim 1.

c. Missing Data

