Specific Aim 1 (Primary Outcome): General linear mixed models (GLMMs) models will be used to compare the primary outcome of alveolar volume (V_A) between the eCPAP and CPAP discontinuation group while adjusting for gestational age at delivery (randomization stratification variable) and other baseline variables that are found to be statistically different between the two groups. Since the lung function measures are highly dependent on infant length and sex, we will further adjust for length and sex in the GLMMs as indicated. In order to adjust for intra-twin correlations, generalized estimating equations (GEEs) with the linear link function will be used to model V_A . The GLMMs can be performed using the GEE estimation approach. Intention to treat analysis will be used for the primary analysis of all aims.

Specific Aim 2 (Secondary Outcomes): Lung diffusion capacity (DLCO) and forced expiratory flows (FEFs) and specifically FEF $_{50}$ will be analyzed with the same general approaches described for the primary outcome of V_A in Specific Aim 1.

FRC measurements in the NICU done pre and post randomization and FEF₂₅₋₇₅, FEF₇₅ done at 6 months of corrected age will be analyzed with the same general approaches as above in Specific Aim 1.

Specific Aim 3 (Exploratory Outcomes): Logistic regression models will be used to compare the incidence of wheeze and the incidence of wheeze and cough between the two groups adjusting for gestational age at delivery (See appendix for standardized respiratory questionnaire administered). Neurodevelopmental scores will be analyzed with the same general approaches described for the primary outcome of V_A in Specific Aim 1.

Intention to treat analysis will be used for the primary analysis of all aims. In addition, all of the aims will also be analyzed with the same general approach using a per protocol analysis and "as treated analysis".

Sample Size and Power Considerations. No studies have compared V_A at 6 months of age in stable infants randomized to eCPAP versus CPAP discontinuation in the NICU. Data from our pilot eCPAP study showed a 12% higher FRC in infants randomized to eCPAP at the end of two week treatment period¹. A study by [name] et al reported a 16% difference in both V_A and D_L in preterm infants according to CPAP treatment in the NICU (Table 1)² and a 12% difference in D_L between infants with BPD versus healthy term infants³. Therefore,

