we powered our randomized trial to detect a 12% difference in V_A between the eCPAP and CPAP discontinuation groups.

Using ANCOVA model and assuming a mean V_A of 642 mL (SD=189) based on data of the overall mean and SD from the

Table 1. Estimated power for 34 infants per group with completed PFT data

Macan (SD) in _____ Estimated Power for Group Differences

Outcome Measures	Mean (SD) in Control Group	Estimated Power for Group Differences		
		12%	15%	17%
Alveolar volume (V _A)	642 (189)	80	92	97
Lung diffusing capacity (D _L)	4.1 (1.19)	80	92	98
Forced Expiratory Flow (FEF ₅₀)	346 (129)	35	49	60

control and CPAP groups reported in Assaf et al², a sample size of 34 infants per group is needed to yield 80% power for detecting a 12% difference (effect size=0.42) in V_A in the eCPAP group at α =0.05. This sample size also allows us to detect a 12% difference in D_L with an effect size of 0.42. We estimate that 18% of the study patients will be twin pairs based on our pilot eCPAP study. Conservatively counting just one infant out of each twin pair for sample size estimation, we will need 38 infants per group (76 total infants at 6 months) with completed V_A outcomes. We further assume a 10% missing data in the NICU (unsuccessful test or infants transferred to another facility) and a 15% loss from NICU discharge to the 6 month PFT (cohort loss, unacceptable PFT, unsuccessful sedation) and therefore we will need to randomize and/or assign 50 infants per group (total n=100) into the trial. This sample size will provide 80% power for detecting an effect size difference of 0.42 in outcome measures between the two groups in Aim 1 (primary outcome of V_A) and Aim 2 for D_L . This sample size allows us to detect a 23% difference in FEF₅₀.

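### The 80% power for a 12% V_A difference at 34 per group depends on a large covariate gain that neither document states

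*Protocol*

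**What the plan says.** Protocol section 7a bases the sample size on an ANCOVA with a mean V_A of 642 mL and an SD of 189 mL, and concludes that "a sample size of 34 infants per group is needed to yield 80% power for detecting a 12% difference (effect size=0.42") at alpha 0.05. It describes the 642 (189) as "the overall mean and SD from the control and CPAP groups" of an earlier cohort, which the protocol tabulates in section 2 b3b, Table 1. The footnote to that table reads "Values are Mean ± SD; p values adjusted for length and gender".

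The SAP repeats the calculation and adds "This sample size will provide 80% power for detecting an effect size difference of 0.42 in outcome measures between the two groups" for V_A and D_L. Its Table 1, titled "Estimated power for 34 infants per group with completed PFT data", prints power for differences of 12%, 15% and 17%: 80/92/97 for V_A, 80/92/98 for D_L and 35/49/60 for FEF50. For FEF50 the text also says "This sample size allows us to detect a 23% difference".

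On the analysis model, Protocol 7 b1 says "Since the lung function measures are highly dependent on infant length and sex, we will further adjust for length and sex in the GLMMs". The SAP, under Specific Aim 1, says "we will further adjust for length and sex in the GLMMs as indicated". It does not define what would count as an indication.

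**The concern.** Anyone who puts the printed mean, SD, difference, sample size and alpha into a power formula gets about half of the printed power. Naming ANCOVA can explain the gap, but only through the share of variance that the covariates remove, and that number is missing. Neither document says whether alpha is one- or two-sided, and the aims are worded directionally.

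The sample size starts from this figure. The 34 per group becomes 38 after the twin allowance. Then 76 / (0.90 × 0.85) = 99.3, which gives the 100 to be randomised. If the assumed covariate gain is too optimistic, a null result would say little about a 12% effect, and a reader could not tell. The SAP's qualifier adds to the problem, because it can be read as allowing the primary V_A model to leave out the two covariates that the 80% most plausibly relies on.

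**Working it through.** **Inputs.** Mean 642 mL, SD 189 mL, 12% difference, 34 per group, alpha 0.05 (Protocol 7a; SAP sample size section). Group values from Protocol Table 1: 606.8 ± 171.5 (n = 29) and 694.6 ± 205.2 (n = 19).

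**Is 189 a raw SD?** The combined mean is (29 × 606.8 + 19 × 694.6) / 48 = 641.6. The overall SD, from the within- and between-group sums of squares, is 188.5. These match 642 (189). The inputs to that SD are unadjusted; the footnote applies the adjustment to the p values only.

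**Effect size.** 0.12 × 642 = 77.0 mL, and 77.0 / 189 = 0.408. The plan prints 0.42.

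**Power without covariate gain.** Noncentral t, df = 2n − 2, noncentrality d × √(n/2). For n = 34 and d = 0.408 the noncentrality is 0.408 × √17 = 1.68.

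| n per group | d | Two-sided | One-sided |
|---|---|---|---|
| 34 | 0.408 | 38% | 51% |
| 34 | 0.42 | 40% | 53% |
| 38 | 0.408 | 42% | – |
| 38 | 0.42 | 44% | – |

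**What ANCOVA must supply.** With residual SD = 189 × √(1 − R²), the effect size needed for 80% power, d*, gives R² = 1 − (d/d*)².

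- n = 34, two-sided: d* = 0.690. R² = 1 − (0.408/0.690)² ≈ 0.65 (residual SD about 112 mL). With d = 0.42, R² = 0.63 (about 115 mL).
- n = 34, one-sided: d* = 0.609. R² = 0.55, or 0.52-0.53 with d = 0.42.
- n = 38, two-sided: d* = 0.651. R² = 0.61, or 0.58 with d = 0.42.

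Taking 3 degrees of freedom for covariates changes power by no more than 0.001.

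**Reproducing the printed V_A row (80/92/97).** Two-sided, R² = 0.63 gives 78/92.5/97 and R² = 0.65 gives 80/94/98. One-sided, R² = 0.55 gives 80/93/97. A large R² was probably used, but the row does not settle which value or which sidedness.

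**FEF50 (mean 346, SD 129, n = 34).** Two-sided, the printed 35/49/60 solve to R² = 0.31/0.29/0.30. If the 23% statement is read at 80% power, it solves to 0.20. One-sided, the row solves to R² between −0.09 and 0.04, and 23% gives 81% power at R² = 0. On either reading the implied R² is far below the one needed for V_A.

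**Sensitivity for V_A (34 per group, d = 0.408).**

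| R² | Power for 12%, two-sided | Power for 12%, one-sided | Detectable at 80%, two-sided |
|---|---|---|---|
| 0 | 38% | 51% | 20% (130 mL) |
| 0.3 | 51% | 63% | 17% (109 mL) |
| 0.4 | 57% | 69% | 16% (101 mL) |
| 0.5 | 65% | 76% | 14% (92 mL) |
| 0.6 | 74% | 84% | 13% (82 mL) |
| 0.65 | 80% | 88% | 12% (77 mL) |

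At 38 per group the two-sided powers are 42, 55, 62, 70, 79 and 84%.

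**The case against.** The best defence is that this is an undisclosed input and not a wrong sum. ANCOVA is named, the protocol says that lung function depends strongly on length and sex, and the V_A and D_L rows fit nearly the same R-squared. That suggests a coherent calculation with one line left out. The value may come from the cited cohort, and nothing in the documents makes 0.63-0.65 implausible. All of this stands, and it is why the point is not that the trial is underpowered. It does not close the gap: the stated power does not follow from the stated inputs, and a qualitative remark about length and sex does not support a specific R-squared.

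Other objections have partial force:

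- The cohort was measured at a mean of 13.7 months and the trial measures at about 6 months corrected age. Both the SD and the R-squared could differ, so 38% is a lower limit only if 189 mL carries over.
- R-squared may legitimately differ by outcome, and the FEF50 row fits a two-sided test better than a one-sided one. The FEF50 figures therefore do not contradict the V_A figures. They show that one unstated value cannot serve all outcomes.
- The pooled within-group SD in Protocol Table 1 is 185.4 mL, which gives 77.0 / 185.4 = 0.416 and may be where 0.42 came from. That is still a raw SD and not the one printed, and the difference is too small to explain the shortfall.
- Thirty-eight per group is the planned number of infants, but 34 is the plan's own count after allowing for twins.
- The SAP still says that it will adjust, so omitting length and sex is a possible reading and not a stated plan.

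**Conclusion.** The concern holds. From the printed inputs, power for a 12% V_A difference at 34 per group is 38% two-sided or 51% one-sided before adjustment, against a stated 80%. Reaching 80% requires covariates to remove about 63-65% of the variance two-sided, or 52-55% one-sided. Neither document states or sources such a figure. True power may be 80%, but the documents do not allow a reader to confirm it, and plausible values of R-squared move it by tens of percentage points. The results assume that the SD of 189 mL applies at 6 months, that allocation is equal, and that the infants counted are independent. The SAP's undefined qualifier makes the gap matter more, because it loosens an adjustment that the protocol makes unconditional. This should be fixed, though it is not a reason to change the sample size.

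**What to change.** Keep N = 100.

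1. In both documents, give the effect size for 77.0 mL over 189 mL as 0.41. State whether alpha is one- or two-sided. For V_A, D_L and FEF50, state the R-squared or residual SD used and its source.
2. Replace the single 80% for V_A with power conditional on R-squared. Two-sided at 34 per group, for R-squared 0, 0.3, 0.4, 0.5, 0.6 and 0.65, power is 38, 51, 57, 65, 74 and 80%. The matching detectable differences are about 20, 17, 16, 14, 13 and 12%.
3. Delete the words *as indicated* from the SAP's Specific Aim 1 paragraph, so that length and sex are always in the primary V_A model, as in the protocol. The same edit is a chance to say which length measurement is meant, since neither document does.

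The cost is wording in two documents, with no extra infants. The stated power becomes conditional and less favourable, and the analyst gives up discretion over two covariates.

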No testing will be done within 3 weeks of a respiratory illness. A test may be repeated if the quality was not acceptable. This testing will include the measurement of alveolar volume (VA), pulmonary diffusing capacity (DI), ^{5;15} forced expiratory flows (FEFs), ⁸⁴ and functional residual capacity ^{93;94} following the guidelines of the American Thoracic Society and European Respiratory Society which were co-written by [name] ^{74;81}. The pulmonary function testing equipment and operational procedures will be rigorously calibrated according to the manufacturer's directions and outlined explicitly in the operations manual. The OHSU Pediatric Sedation Protocol will be followed using oral chloral hydrate. The infant will be given 50 to 100 milligrams per kilogram of chloral hydrate by mouth, with a maximum dose of 1 gram. The parents will be counseled about possible side effects including temporary disorientation, nervousness, excitement, dizziness, coughing, nausea, mild desaturations, obstruction of airway, apnea and will be asked to sign a separate consent for sedation. They also will also be given patient education-discharge instructions. Adverse events will be reported as outlined below. For pulmonary function measurements with published normative data, the parents will be told whether the results of the pulmonary function test were within normal limits or outside of normal limits, and this report will be faxed to the patient's physician. The hemoglobin level will also be shared with the parent and if outside of normal limits for the CGA will be relayed to the infant's physician.

Alveolar Volume (V_A) (**Primary Outcome of Study**) and: Pulmonary Diffusing Capacity (D_L)(**Secondary Outcome**): Measurements will be obtained using an induced respiratory pause technique at an elevated lung volume (30 cm of H_2O) that we developed and have previously described^{5;68} as approved in OHSU eIRB# 386. The inspiratory test gas contains 0.5% Ne (neon), 0.5% CO (carbon monoxide), 21% O_2 (oxygen) and balance N_2 (nitrogen). Concentrations of CO and Ne are measured with a gas chromatograph. During passive expiration following the 4-second induced respiratory pause for gas exchange, CO and Ne concentrations are used to calculate V_A and D_L . Results are expressed as averages of 2-3 measurements within 10%, adjusting for Hemoglobin from a finger stick.

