We anticipate loss to follow-up for the lung function outcomes at 6 months and respiratory outcomes through 12 month of age. Our sample size estimation conservatively accounts for 10% cohort loss from randomization to NICU discharge and a 15% loss from discharge until the 6 month PFTs. However based on VCSIP, which had a 93% cohort retention for attempted of 3 month PFTs⁸⁴, coupled with our retention techniques, we suspect this will be overestimated but want to ensure an adequate sample size for analysis of the primary outcome. We will compare patients' characteristics at baseline between those with outcome measures and those lost to follow-up and determine whether the missing data differ between the groups. If the missing at random assumption is violated, we will conduct extensive sensitivity analyses to model various non-ignorable missing data patterns to examine the robustness of our findings to the various missing data assumption¹⁰⁰.

d. Interim analysis and stopping rules

No interim analysis for efficacy or futility is planned. There will be no pre-specified stopping rules, but the DSMB will review SAEs as they occur. Although this is a fragile population, based on our pilot CPAP study, the fact that infants will be convalescing by the time they are enrolled in the study, and our experience with sedation in the VCSIP⁸⁴, we do not anticipate a large number of SAEs but will be vigilantly monitoring. The DSMB chair may call a DSMB meeting to specifically review safety concerns.

8. Data and Specimens

a. Handling of Data and Specimens

All data will be stored in locking file cabinets and contained within a password protected database. Neonatal and follow-up data from all patients consented for participation into the study will be recorded on forms designed specifically for this study. A screening log of all preterm infants who qualify for randomization to eCPAP versus dCPAP will be kept to determine the generalizability of the population. All data will be entered electronically by the research staff into the secure REDCap system. Data will be store indefinitely.

b. Sharing of Results with Subjects

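### Missing-data sensitivity analyses for alveolar volume hang on a condition the trial's data cannot test, so the primary result may get no robustness check

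*Protocol*

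**What the plan says.** Protocol section 7.c (Missing Data) budgets for "10% cohort loss from randomization to NICU discharge and a 15% loss from discharge until the 6 month PFTs". It adds of that allowance that "we suspect this will be overestimated but want to ensure an adequate sample size for analysis of the primary outcome", pointing to "93% cohort retention for attempted of 3 month PFTs" in the investigators' earlier vitamin C trial.

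Two checks follow. The first is "We will compare patients' characteristics at baseline between those with outcome measures and those lost to follow-up". The second asks whether missing data differ between the groups. The next sentence carries the condition: "If the missing at random assumption is violated, we will conduct extensive sensitivity analyses to model various non-ignorable missing data patterns". No criterion for declaring a violation is given, no specific method is named, and no range of departures is set.

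For the primary analysis, Protocol section 7.b1 states "The intention to treat population is defined as all randomized infants" and analyses V_A by GEE, adjusting for gestational age stratum, length, sex and any baseline variables found to differ. No imputation or weighting is mentioned.

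The SAP of August 2023 repeats the model and has no missing-data section. It uses the loss figures only in Sample Size and Power Considerations, where it says "We further assume a 10% missing data in the NICU" and attributes this to unsuccessful tests or transfers. It adds per-protocol and as-treated analyses. Under Population it defines a set of infants with completed V_A, tested at 4 to 12 months corrected age.

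**The concern.** A sensitivity analysis for missing data exists because the assumption behind the main analysis cannot be verified. Making it conditional on that assumption being shown false defeats its purpose. The likely outcomes are that it is never triggered, or that it is triggered by something else, such as a baseline difference that is fully compatible with missing at random.

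The plan gives reasons why missing V_A might relate to lung health. Protocol section 6.d says "No testing will be done within 3 weeks of a respiratory illness", and section 7.a names this need to wait after a respiratory infection among the reasons for the 15% loss. Aim 3 asks whether extended CPAP lowers respiratory morbidity. If it does, the infants who reach a valid test could differ between arms, and the comparison of tested infants would then be biased. The direction would depend on the arm affected.

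**Working it through.** **1. Reproduce the planned loss.** Inputs: 10% then 15% loss, 38 infants per group (76 in total) with V_A, 100 randomised (Protocol 7.a and 7.c; SAP, Sample Size and Power Considerations).

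- Retention = 0.90 x 0.85 = 0.765, so loss = 23.5%.
- 76 / 0.765 = 99.3, rounded up to 100. 38 / 0.765 = 49.7, rounded up to 50 per group. Both match the plan.

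**2. Smaller losses the protocol makes plausible.**

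- 93% retention overall: loss = 7%.
- 10% NICU loss, then 93% retention: 1 - 0.90 x 0.93 = 16.3%.

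**3. Can the condition be evaluated?**

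| Planned check | What it can show | What it cannot show |
|---|---|---|
| Baseline characteristics, tested versus lost | Data are not missing completely at random | Whether missingness depends on V_A itself, given what was observed |
| Whether missing data differ between the groups | Unequal amounts or patterns of missingness | The same |

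A positive result in either row is compatible with missing at random. A negative result does not exclude missing not at random. Nothing in the plan maps a result to a declared violation.

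**4. Is missing at random the right threshold for this model?** The GEE has one V_A per infant and, as described, uses only infants with a value. It is protected if missingness depends only on covariates in the model. Respiratory illness after discharge is recorded monthly (Protocol 6.e) but is not in the model. If testing depends on that illness, and the illness is related to V_A, the estimate can be biased even though the data are missing at random given the questionnaires. The condition would then not be met.

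**5. Illustrative size.** Let m be the fraction missing in an arm and d the amount by which untested infants fall below tested infants in that arm. Then

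bias of the complete-case difference (eCPAP minus dCPAP) = m_E x d_E - m_D x d_D.

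Inputs: SD 189 mL and target 0.12 x 642 = 77 mL (Protocol 7.a). The assumed shift, 0.25 to 0.5 SD (47 to 94.5 mL) in one arm and zero in the other, is not from the documents.

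| Missing in the affected arm | Bias at 0.25 SD | Bias at 0.5 SD | Share of 77 mL |
|---|---|---|---|
| 23.5% | 0.235 x 0.25 x 189 = 11.1 mL | 0.235 x 0.5 x 189 = 22.2 mL | 14% to 29% |
| 16.3% | 7.7 mL | 15.4 mL | 10% to 20% |
| 7% | 3.3 mL | 6.6 mL | 4% to 9% |

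The primary model adjusts for length and sex, so the relevant SD is smaller. The documents give no adjusted SD. If covariates explained 64% of the variance (an assumption, close to what 34 per group would need for 80% power at 77 mL), the SD would be 189 x sqrt(0.36) = 113 mL. The 23.5% row would become 6.7 to 13.3 mL, or 9% to 17% of the target.

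**The case against.** Several points on the other side are sound.

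- **The loss may be much smaller.** A reader might infer that the primary result will lack 23.5% of infants. The documents do not support that: it is a deliberately conservative allowance. The SAP's 10% also includes unsuccessful NICU tests, and a failed NICU test need not mean a missing 6-month V_A. In the other direction, the 93% comparator is for attempted 3-month tests, not acceptable 6-month V_A measurements.
- **Missingness is examined.** It would be wrong to say that the plan ignores it. The second check may well mean differences between treatment arms. It remains a description of who is missing, and does not stress-test the treatment effect.
- **The illness mechanism is not established.** The 3-week rule defers testing; it does not exclude the infant. A test of unacceptable quality may be repeated. The SAP widens the V_A window to 4 to 12 months, from 5 to 8 months in Protocol 6.d, and its list of reasons for the 15% loss no longer names respiratory infection. Illness-related loss is possible, but the documents do not show it to be a main cause.
- **There is no hidden contradiction in the ITT definition.** A reader might see one between all randomised infants and a model fitted to tested infants. Protocol 7.b1 uses ITT to fix analysis by assigned arm, and the SAP openly defines a V_A-completed set.
- **The bias scenario is one-sided by construction.** Equal departures with equal missingness in the two arms cancel.

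These points limit the likely size of the problem. They do not supply a trigger that works or a method in the SAP.

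**Conclusion.** The concern holds in a limited form. The rule in Protocol 7.c cannot be applied as written, because the data that would show a violation are the data that are missing. The later SAP contains nothing to replace it, and its per-protocol and as-treated analyses do not address missing V_A. A primary result on tested infants may therefore be reported with no robustness check.

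The conclusion about the rule rests on logic and needs no numerical assumption. The size does: about 11 to 22 mL at the projected upper loss of 23.5%, and about 3 to 7 mL at 7%, if untested infants in one arm only were 0.25 to 0.5 SD lower on the unadjusted SD. It would be less with a length-adjusted SD. These figures show what an unexamined departure could do. They do not estimate the bias in this trial, and nothing here shows that the result will be biased.

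**What to change.** Delete the condition. Before unblinding, add a missing-data section to the SAP that applies to V_A in every case:

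1. **Multiple imputation for all randomised infants.** The imputation model should contain treatment arm, all primary-model covariates (gestational age stratum, sex, length, and any baseline variables added for imbalance), the NICU FRC measurements and the monthly respiratory questionnaire data. Where the test visit did not take place, length at that visit must itself be imputed. The model must respect twin clustering, since the plan expects 18% of the sample to be twin pairs.
2. **A delta-adjusted tipping-point analysis.** Shift the imputed V_A over a range fixed in advance, for example 0 to 0.5 SD, separately in each arm. Report the shift at which the conclusion changes, or that it does not change within the range.

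Keep the complete-case GEE as the primary analysis, and keep the two descriptive checks alongside it.

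The cost is SAP wording and some programming. No new data are needed and the sample size stays at 100. The drawback is that the conclusion may look less certain if it tips at a small shift.
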